#### **3.1.4** General Considerations

General considerations for descriptive statistics and presentation for continuous and categorical data are given below.

#### 3.1.4.1 Continuous variables

Continuous data will be described using descriptive statistics: number of observations (n), mean, standard deviation, median, minimum, and maximum.

Means, medians, standard deviations, and confidence intervals (CIs) will be reported to one decimal place more than the data reported on the case report form (CRF) or by the vendor. Minimum and maximum will be reported to the same number of decimal places displayed on the CRF or by the vendor. P-values will be reported to 4 decimal places.

#### 3.1.4.2 Binary Endpoint and Other Categorical Variables

For endpoints with two possible outcomes such as alive/otherwise or response/otherwise within specific periods, the 95% confidence interval will be calculated with Clopper-Pearson method for survival rates or response rates. For

other categorical variables, the counts and percent of each category within a parameter will be calculated for observed data only. The denominator for all percentages, unless otherwise specified, will be the number of subjects in the cohort or in the specified analysis population.

#### 3.1.4.3 Progression-Free Survival (PFS) Endpoints

PFS is defined as the time from date of first dose to the date of disease progression or death, whichever happens first. For subjects who do not have an event (i.e. those who have not progressed, and are alive at the date of data cut-off or lost to follow-up), progression-free survival will be censored on that date.

PFS will be summarized using Kaplan-Meier methods for 25th percentile, median, and 75th percentile. 95% Confidence intervals will be calculated using Greenwood Formulation. Kaplan-Meier curves will be plotted for populations in the analysis.

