## 13.4.6. Efficacy/Activity

## **13.4.6.1.** Primary efficacy endpoint

## Progression-Free Survival at 6 months (PFS-6).

PFS is defined as the time between date of first dose and the date of first documented disease progression or death, whichever occurs first. The PFS-6 is defined as a patient being alive and progression free at 6 months (24 weeks). Disease progression will be determined based on investigator assessment with use of radiological assessments, clinical status, and corticosteroid

use. The specific criteria for disease progression is defined in Appendix 2. Patients without a date of disease progression or death will be analyzed as censored observations on the date of the last disease assessment; if no post-baseline disease assessment is available, PFS will be censored at the date of 1st dose.

The analysis of the primary endpoint and the estimation of PFS-6 is performed with a Cox model. Karnofsky performance status is included as a covariate. Study center is included as a random effect assumed to follow a gamma distribution. Thus, this is a shared Cox gamma frailty model. The model is used to estimate PFS-6 with 2-sided 95% and 90% confidence intervals.

Furthermore, Kaplan-Meier methodology will be used to estimate median PFS with 95% CI and the Kaplan-Meier curve will be constructed to provide a visual description of the PFS over time.

Descriptive statistics overall and for each parameter (radiological assessment, clinical status and corticosteroid dose) in the disease progression assessment are presented for the entire assessment period as well as for 3, 6 and 9-month time points.

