where ORR is defined as a CR or PR. Patients without a post-baseline disease assessment will be considered as non-responders. The analysis population for ORR will be all enrolled patients with measurable disease at baseline. An estimate of ORR and its 95% CI will be calculated using the Blyth-Still-Casella method for each treatment arm. CIs for the difference in ORRs between the subgroups will be determined using the normal approximation to the binomial distribution. In addition, ORR is analyzed with a generalized logistic regression analysis. Subgroup is included as fixed effect, KPS as a covariate and study center as random effect. The adjusted odds ratio for being a responder is estimated and the two-sided 95% confidence interval presented.

DOR is defined as the time from the initial response to disease progression or death among patients who have experienced a CR or PR during study. Patients who have not progressed or died at the time of analysis will be censored at the last disease assessment date. DOR will be estimated using Kaplan- Meier methodology. Comparisons between subgroups through use of the unstratified log-rank test will be made for descriptive purposes only.

- To evaluate the efficacy of tesevatinib as measured by PFS-6, OS-9, RANO ORR and DOR in the subgroups:
  - EGFRvIIIpos vs EGFRvIIIneg
  - EGFR amplificationpos vs EGFR amplificationneg

The statistics for these subgroup comparisons are described at each of the endpoints.

In addition, statistics for the change and percent change from baseline tumor measurements will be presented. These analyses will be done after each two cycles of therapy. Summary statistics will be produced for PFS and OS. The percentage of patients without disease progression after 3 and 6 months of dosing will also be presented separately by local (investigator) and potentially by central radiography results. Sites will provide copies of all MRI image sets for central retention in case central radiology review is required.

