## 3.1.2 Changes from protocol

Changes from protocol in statistical methods are made in both primary and secondary analyses wherever necessary.

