#### 3.1.4.4 Overall Survival (OS) Endpoints

OS is defined as the time from first dose until death due to any cause. In absence of confirmation of death, subjects will be censored either at the date that the subject was last known to be alive or the date of study cut-off, whichever comes earlier.

OS will be summarized using Kaplan-Meier methods for 25th percentile, median, and 75th percentile. 95% Confidence intervals will be calculated using Greenwood Formulation. Kaplan-Meier curves will be plotted for populations in the analysis.

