#### Missing event dates

Event date will be imputed only when day is missing, and the purpose of imputing an event date is to most conservatively calculate time to event.

If the day is missing, the first (mid, last) day of the month will be imputed for undesired (neutral, desired) event. If the missing day is the same as the month of first dose of study drug, then the first dose date will be imputed for undesired event.

These data imputations are for time to event calculation only and will not be used in the listings.

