## **3.8 Primary Endpoint Analysis**

## 3.8.1 Progression-Free Survival Rate at 6 Month (PFS-6)

Proportion of patients who are alive and not progressed at 6 months (24 weeks) will be analyzed with method as described in3.1.4.2. This analysis is based on mITT population. Patients whose survival or response status at 6 months (24 weeks) are unknown are not considered alive or progression free. Response Assessment in Neuro-Oncology (RANO) criteria are used to determine specific criteria for treatment response (Appendix 2 of the protocol.) in all endpoint analysis in this study.

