## 3.8.2.5 Objective Response Rate (ORR) and DOR per RANO

ORR including CR or PR per RANO criteria will be analyzed with method as described in 3.1.4.2 respectively in subpopulations A and B, and in mITT population. This analysis will be performed in subpopulations A and B, and in mITT population.

For responders in above analyses, corresponding Duration of response is calculated as the time from first documented evidence of CR or PR (whichever status is recorded first) until the first documented sign of disease progression or death due to any cause (whichever is the first). DOR will be summarized

It is defined for subjects with a confirmed CR or a confirmed PR. For subjects in the subset of responders who do not progress or die, duration of response will be analyzed with method as described in 3.1.4.3.

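### The SAP censors secondary Kaplan-Meier PFS and DOR at data cut-off or loss to follow-up instead of the protocol's last disease assessment, without declaring the change, so time after the last scan counts as progression-free

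*SAP*

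**What the plan says.** Protocol 13.4.6.1 sets the PFS rule: "Patients without a date of disease progression or death will be analyzed as censored observations on the date of the last disease assessment". A patient with no post-baseline assessment is censored at first dose. For DOR, protocol 13.4.6.2 says: "Patients who have not progressed or died at the time of analysis will be censored at the last disease assessment date".

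SAP 3.1.4.3 moves the date. It says of patients without an event who "are alive at the date of data cut-off or lost to follow-up), progression-free survival will be censored on that date". SAP 3.8.2.3 uses this for PFS in the mITT population and in Subpopulations A and B. For responders who neither progress nor die, SAP 3.8.2.5 says that "duration of response will be analyzed with method as described in 3.1.4.3". Neither SAP section mentions the last disease assessment or the first-dose fallback.

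The only SAP text on departures from the protocol is the general statement in 3.1.2: "Changes from protocol in statistical methods are made in both primary and secondary analyses wherever necessary". It names no change and gives no reason.

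**The concern.** Death is dated whenever it happens, but progression is mainly found at a disease assessment. A patient whose scans have stopped is no longer under observation for progression. Under the SAP rule that patient stays in the risk set as progression-free until cut-off or loss to follow-up.

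The SAP does limit follow-up for overall survival. In 3.1.4.4, without confirmed death, "subjects will be censored either at the date that the subject was last known to be alive or the date of study cut-off", whichever is earlier. PFS has no matching limit at the date last known progression-free. The rule also sits badly beside SAP 3.1.7, which says of missing event dates that "the purpose of imputing an event date is to most conservatively calculate time to event".

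At stake are the secondary PFS quartiles, the plotted PFS curves and DOR. This is a single-arm trial, so no control arm shares the bias. The primary endpoint is not at stake, because SAP 3.8.1 analyses PFS-6 as a proportion and states: "Patients whose survival or response status at 6 months (24 weeks) are unknown are not considered alive or progression free".

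**Working it through.** **1. The rules side by side**

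| Case | Protocol | SAP |
|---|---|---|
| PFS, no event | last disease assessment | data cut-off or loss to follow-up |
| PFS, no post-baseline assessment | first dose | no separate rule |
| DOR, no event | last disease assessment | as for PFS |
| Change listed in SAP 3.1.2 | – | no |

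**2. Direction.** The Kaplan-Meier estimate is S(t) = ∏(1 − d_j/n_j), where d_j is the number of events and n_j the number at risk at event time j. Both rules use the same events. Later censoring can only leave n_j unchanged or increase it, so each factor, and hence S(t), stays the same or rises.

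**3. Can scan-free time arise?** The documents pull in different directions. Protocol 10 requires scans every 8 weeks until progression. The protocol synopsis says that long-term follow-up is no longer required as of Amendment 4. SAP 2.2 describes only 30 days of follow-up after the last dose, or until a new treatment starts.

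**4. Design distribution.** Protocol 13.2 gives median PFS 4.5 months, PFS-6 25% and Weibull parameters 5.24 and 2.41. These reproduce with shape 2.41 and scale 5.24 months (the table's labels are the other way round):
- Median = 5.24 × (ln 2)^(1/2.41) = 4.50 months.
- S(6) = exp[−(6/5.24)^2.41] = 0.250.
- At 24 weeks (168/30.4375 = 5.52 months), S = exp[−(5.52/5.24)^2.41] = 0.322.

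A curve read at day 182 shows the week-24 scan, so the reference value is 32.2%, not 25%.

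**5. Simulation.** There were 1,500 trials of 40 patients per scenario and stopping rate. From the documents: the Weibull above; progression dated at scans in weeks 4, 8, 16, 24 and every 8 weeks; and cut-off six months after the last patient starts (protocol 13.4.1). Assumed: uniform 12-month accrual, and 10% or 20% of patients stopping scans in weeks 2–16. Kaplan-Meier PFS at day 182, protocol rule against SAP rule (differences taken before rounding):

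| Scenario | 10% stop | 20% stop |
|---|---|---|
| (a) scans continue to cut-off (nobody stops) | 0.322 vs 0.322 | same |
| (b) censored 30 days after scans stop | 0.320 vs 0.326 (+0.5 points) | 0.321 vs 0.331 (+1.1) |
| (c) carried to cut-off, later deaths captured (assumed median 5 months after progression) | 0.342 vs 0.369 (+2.7) | 0.359 vs 0.411 (+5.2) |
| (d) carried to cut-off, no later deaths captured | 0.322 vs 0.386 (+6.3) | 0.320 vs 0.448 (+12.7) |

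In (c), assumed medians of 3 to 8 months give +1.9 to +3.6 points at 10% and +3.6 to +6.9 at 20%.

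**6. Quantities the SAP tabulates.** The typical estimated median is 5.5 months under both rules in every scenario. It moved in 0.7–5.3% of trials at 10% stopping and in 2.5–21% at 20%. The typical 75% event time moves only in (d) at 20%, from 7.4 to 9.2 months. There it is not reached in 20% of trials under the SAP rule, while under the protocol rule it is always reached.

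**7. Other assumptions.** With 18-month accrual, stopping spread over months 0–6 and no later deaths captured, PFS at 6.0 months was 0.346 vs 0.321 at 5% stopping, 0.369 vs 0.319 at 10%, 0.421 vs 0.323 at 20% and 0.468 vs 0.320 at 30%. That is about 2.5 to 15 points higher under the SAP rule. The mean estimated median went from 5.49 months under the protocol rule to 5.50, 5.54, 5.73 and 6.04 months.

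DOR is not quantified, because the documents give no expected response rate or duration.

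**The case against.** The wording plainly differs; the dispute is about size.

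- **The point shifts are in a figure the SAP does not tabulate.** SAP 3.1.4.3 asks for quartiles and curves, and the typical median does not move. This stands for the tables. The plotted curve is still affected.
- **Scenario (d) strains the clause.** Only patients alive at cut-off are carried that far. Someone whose death would go unrecorded is more naturally lost to follow-up and censored at that date. This stands to the extent that (d) is an upper bound. The SAP does not define the date of loss to follow-up, and gives no date for patients who withdraw, whom protocol 8.4 lists separately.
- **Scenario (c) needs scans to stop while contact continues.** The protocol asks for both until progression or new therapy. If follow-up instead ends 30 days after the last dose, (b) is the closest case and the shift is about one point or less. This is fair, and the documents do not settle which applies.
- **Some reasons for stopping scans are already events.** Protocol Appendix 2 counts failure to return because of death or deterioration as progression, and the synopsis counts need for radiation. Protocol 12.2.14 dates progression at the most recent MRI when new therapy starts without it. So 10–20% may be too high. The SAP does not restate the new-therapy rule, however.
- **SAP 3.1.7 concerns a missing day in an event date, not censoring.** This stands. It shows a contrast of intent, not a breach.
- **The protocol rule does not remove all bias.** In (c) at 20% it gives 0.359 against 0.322, so 3.7 points remain. This also stands: missed scans followed by recorded deaths inflate PFS under either rule.

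None of this supports the SAP's date over the protocol's, or explains why the change is undeclared.

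**Conclusion.** The concern holds and should be fixed. The mismatch, its reach to both secondary PFS and DOR, and its direction follow from the text and from the Kaplan-Meier formula; confidence in these is high. The size is uncertain because it rests on an assumed share of patients who stop scans without progression. It is zero with full scanning, about 0.5 to 1.1 points at day 182 if censoring follows 30 days after scans stop, 2.7 to 5.2 points in (c), and at most 6.3 to 12.7 points in (d), at 10% and 20% stopping. The effect is confined to secondary, unpowered summaries.

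**What to change.** In SAP 3.1.4.3 and 3.8.2.5, restore censoring at the last evaluable disease assessment, with first dose as the PFS censoring date if there is none. Cross-refer to protocol 12.2.14 for dating progression when new anti-cancer therapy starts without it. Keep the rule based on last known alive or cut-off for OS only. List any departure that is kept in SAP 3.1.2 with its reason, and retain cut-off censoring at most as a labelled sensitivity analysis.

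The cost is a few sentences in the SAP and no new data. PFS and DOR estimates will be the same or less favourable, depending on how much scan-free time there is.

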#### 3.1.4.4 Overall Survival (OS) Endpoints

OS is defined as the time from first dose until death due to any cause. In absence of confirmation of death, subjects will be censored either at the date that the subject was last known to be alive or the date of study cut-off, whichever comes earlier.

OS will be summarized using Kaplan-Meier methods for 25th percentile, median, and 75th percentile. 95% Confidence intervals will be calculated using Greenwood Formulation. Kaplan-Meier curves will be plotted for populations in the analysis.

#### 3.1.5 Study Day

The Study Day for all assessments prior to the first study drug administration is calculated as the difference between the date of the event or measurement (e.g., adverse event [AE] onset date, assessment date, sample collection date) and the start date of study treatment. The day before the start of study treatment is Study Day -1.

The Study Day for all post-assessments after the first study drug administration is calculated as the difference between the date of the event or measurement (e.g., AE onset date, assessment date, sample collection date) and the start date of study treatment plus one day. The first day of study treatment is Study Day 1 with subsequent study days numbered sequentially thereafter.

#### 3.1.6 Baseline

Baseline value is defined as the valid and last non-missing value obtained within 28 days prior to subject receiving the first study medication, unless otherwise stated under the related assessment section. Baseline can be the day before the first study medication or on the same day as the first study medication if a pre-dose assessment is available. Subjects without data on a parameter before the first study medication will have a missing baseline for this parameter.

## 3.1.7 Handling of Incomplete or Missing Data

Missing data will not be imputed in general and will be reported as missing in all listings. For categorical variables, patients with missing data are not included in calculations of percentages unless otherwise specified.

#### Missing start and end dates for AE and concomitant medication (CM)

The assumption will be the worst or most conservative judgment when imputing AE and CM start and end dates. The purpose of imputing a start date is to help define whether the AE/CM started while taking study drug.

For a partial or missing start date:

- If the day is missing, the first day of the month will be imputed. If the missing day is the same as the month of first dose of study drug, then the first dose date will be imputed.
- If the day and month are missing, the first day of January will be imputed. If the year is the same as the first dose date, then the first dose date will be imputed.
- If the day is completely missing, the first dose date will be imputed. If the end date suggests it could have started prior to this, the first day of January of the same year as the end date will be imputed.
- When imputing a start date, the start date will ensure that the new imputed date is sensible, i.e., is prior to the end date of the AE or CM.

For a partial or missing end date:

- If the day is missing, the last day of the month or the last assessment date, whichever is earlier, will be imputed.
- If the day and month are missing, the 31st of December or the last assessment date, whichever is earlier, will be imputed
- If the date is completely missing, there will be a need to look at whether the AE/CM is still ongoing before imputing a date. If the ongoing flag is missing, then it will be assumed that AE is still present, or CM is still being taken (i.e., do

not impute a date). If the AE/CM has stopped, then the last assessment date will be imputed.

These data imputations are for categorization purpose only and will not be used in the listings.

If the assessment of the relationship of the AE to tesevatinib is missing, then it will be assumed that the AE is related to tesevatinib and the AE considered as such in the frequency tables of possibly related AEs. No imputation should be done at the data level.

#### Missing event dates

Event date will be imputed only when day is missing, and the purpose of imputing an event date is to most conservatively calculate time to event.

If the day is missing, the first (mid, last) day of the month will be imputed for undesired (neutral, desired) event. If the missing day is the same as the month of first dose of study drug, then the first dose date will be imputed for undesired event.

These data imputations are for time to event calculation only and will not be used in the listings.

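### A death or progression with a missing day is dated to the first of the month, with no floor at the last date the patient was known alive or progression-free

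*SAP*

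**What the plan says.** SAP 3.1.7, Missing event dates, covers events for which only the day is unknown:

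- The rule: "If the day is missing, the first (mid, last) day of the month will be imputed for undesired (neutral, desired) event".
- The one floor: if the event month is the month of first dose, "then the first dose date will be imputed for undesired event".
- The aim: "the purpose of imputing an event date is to most conservatively calculate time to event".
- The scope: "These data imputations are for time to event calculation only and will not be used in the listings".

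The SAP does not list which events count as undesired. Death and progression are the natural reading.

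The endpoint definitions add no further bound. In SAP 3.1.4.3, "PFS is defined as the time from date of first dose to the date of disease progression or death, whichever happens first". In SAP 3.1.4.4, "OS is defined as the time from first dose until death due to any cause". DOR (SAP 3.8.2.5) ends at progression or death and is also silent on partial dates.

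Two neighbouring rules do look at other recorded dates. For imputed start dates of adverse events and concomitant medications, "the start date will ensure that the new imputed date is sensible, i.e., is prior to the end date of the AE or CM"; imputed end dates there may not pass the last assessment date. For patients not known to have died, SAP 3.1.4.4 says "subjects will be censored either at the date that the subject was last known to be alive", or at study cut-off if that is earlier.

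**The concern.** The rule can produce an event date that the trial's own data disprove. A patient seen in clinic on the 20th who dies later that month, day unknown, is dated dead on the 1st. Had that patient been lost after the same visit, OS would have been censored at the 20th. Confirmed survival time is thus kept for a censored patient and removed for one who died.

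PFS takes whichever of progression and death comes first. If a scan on the 15th documents progression and death follows in the same month without a day, the imputed death on the 1st becomes the PFS event, ahead of a progression date that is fully known.

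At stake are the Kaplan-Meier summaries of PFS, OS and DOR. The primary endpoint is at stake only on the condition discussed below.

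**Working it through.** No sample size, power or error rate in the plan depends on this rule, so there is no stated figure to reproduce. The check is date arithmetic, followed by two estimates of how often a contradiction would arise **given** a missing day.

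**1. Is there a floor?** In the month of first dose the imputed date is the first dose date. In any later month the 1st already falls after first dose. Time to event can therefore be zero but not negative. No sentence in SAP 3.1.7, 3.1.4.3, 3.1.4.4 or 3.8.2.5 refers to the last date known alive or progression-free.

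**2. Worked dates.** The scan schedule is weeks 4, 8, 16, 24 and so on (Protocol section 10). Assume first dose on 10 January 2017.
- Week-24 scan: 10 January + 168 days = 27 June, progression-free.
- Death on 29 June, 170 days after first dose, day not recorded.
- Imputed date: 1 June, 142 days after first dose.
- The imputed date is 26 days before a scan showing the patient alive and progression-free. Time to event is short by 170 − 142 = 28 days.

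**3. Displaced progression.** Scan-documented progression on the 15th, death later that month with the day missing. Imputed death is the 1st, so PFS ends 15 − 1 = 14 days before the documented progression.

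**4. Simple count.** Assume the day of death is uniform on 1 to 30. The backward shift s is then 0 to 29 days, with mean 14.5. Let the last contact be L days before death. The imputed date precedes that contact when L < s.
- 28-day visits, L uniform on 0 to 27: sum of min(s, 28) over s = 0 to 29 is (0 + 1 + … + 28) + 28 = 406 + 28 = 434 of 30 × 28 = 840 pairs, or 52%.
- 8-weekly scans, L uniform on 0 to 55: 0 + 1 + … + 29 = 435 of 30 × 56 = 1,680 pairs, or 26%.

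**5. Simulation on the planning curve.** Event times were drawn from a Weibull curve matching the planned median PFS of 4.5 months and 6-month PFS of 25% (Protocol 13.2). Shape 2.41 and scale 5.24 months give a median of 5.24 × (ln 2)^(1/2.41) = 4.50 months and exp(−(6/5.24)^2.41) = 0.250. Protocol Table 6 prints these two values under the opposite labels. First doses were assumed uniform over two calendar years, the day was treated as missing for every event, and the first-dose floor was applied. With 400,000 events:

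| Quantity, given a missing day | Result |
|---|---|
| Imputed date before last scheduled scan | 26.7% |
| Imputed date before last 4-weekly visit | 48.6% |
| Mean backward shift | 14.7 days |
| Maximum shift | 30 days |
| First-dose floor applied | 0.6% |
| Negative times | 0 |
| Events truly after day 168 that are dated before day 168 | 20.6% |

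**6. With a floor at the last documented contact.** In the example of step 2 the imputed date becomes 28 June, 169 days against a true 170. By construction no imputed date then precedes such a contact.

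**The case against.** **The rule is deliberately conservative.** In a single-arm trial, shortening PFS and OS by at most 30 days works against the drug. That stands for the overall estimates. It does not justify a date the database rules out. It also does not carry over to the marker-positive versus marker-negative comparisons (SAP 3.8.2.6), where the direction depends on which group has the missing days.

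**The case will be rare.** This largely stands. Progression is normally dated by a scan or visit. Deaths up to 30 days after the last dose must be reported within 24 hours of awareness (Protocol 11.3.11.2), and the sponsor undertakes to find the date of death (Protocol 8.4). On-treatment deaths, to which the 28-day-visit figure applies, are therefore the least likely to lack a day. Month-only dates are more plausible from 8-weekly telephone follow-up, which Amendment 4 no longer requires.

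**The neighbouring rule proves little.** The plausibility check on adverse-event and medication start dates requires only start before end and sets no last-contact floor. This is fair: it shows attention to plausibility, not the missing bound itself.

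Three stronger readings are tempting, and the documents do not support them:

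- *That there is no lower bound at all.* The sentence after the rule sets one at first dose.
- *That PFS-6 is biased.* SAP 3.8.1 analyses a proportion alive and not progressed at 24 weeks, and SAP 3.1.7 confines imputed dates to time-to-event calculation. A patient with a progression-free day-168 scan has a documented status. A flip, worth 1/40 = 2.5 percentage points, needs week-24 status to be derived from the imputed date. The SAP neither says so nor excludes it.
- *That DOR will come out negative because response goes to month end and progression to month start.* DOR is restricted to confirmed responders, and confirmation needs imaging at least 4 weeks later (Protocol 10.1). A first response on day r cannot be confirmed before day r + 28, so progression after confirmation in the same calendar month requires r to be about 3 or less. With 8-weekly scans after week 8, this is nearly excluded.

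**Conclusion.** The defect holds as a gap in the text: the rule permits event dates that contradict a recorded visit, scan or documented progression. **Severity is minor.** For an affected event the loss is up to 30 days and about 15 on average. Given a missing day, roughly a quarter of imputed dates would precede the last scheduled scan and about half would precede the last 4-weekly visit. Those shares rest on the assumed uniform days or the planning curve, and on contacts occurring on schedule up to the event. They are not shares of all patients. The documents do not say how many days will be missing. The effect falls mainly on death dates, hence on OS and on PFS and DOR where death is the event. No consequence for the primary endpoint is established.

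**What to change.** Amend SAP 3.1.7, Missing event dates, to say:

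1. A death with a missing day is dated to the later of the first of the month and the day after the last date known alive. Any documented progression date counts as a date known alive.
2. A progression with a missing day is dated to the later of the first of the month and the day after the last assessment without progression.
3. Neither date may pass the end of the recorded month, and the existing first-dose floor stays.
4. Week-24 PFS status is taken from documented assessments where available, not from an imputed date that contradicts them.

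It would also help to name death and progression as the undesired events. The cost is a few SAP sentences and a few lines of code, using dates already collected. No new data are needed.
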